	Post FVIII Prophylaxis - 52		Days [the later date of Day 33 or 3 days after the end of FVIII prophylaxis, 368]
	Post FVIII Prophylaxis and Beyond		≥ the later date of Day 33 or 3 days after the end of FVIII prophylaxis
Note: all assessments within the above defined windows will be used to derive the corresponding endpoint.			
Number of FVIII infusions, Bleeds	Baseline ^d		< Day 1
	Week 1 – FVIII Prophylaxis End		Days [1, the later date of Day 32 or 2 days after the end of FVIII prophylaxis]
	Post FVIII Prophylaxis - 52		Days [the later date of Day 33 or 3 days after the end of FVIII prophylaxis, 368]

	Study 270-301 Statistical Analysis Plan
---	--

Assessment	Derived Visit	Scheduled Visit Day ^a	Window ^b
	Post FVIII Prophylaxis and Beyond		≥ the later date of Day 33 or 3 days after the end of FVIII prophylaxis
Note: all assessments within the above defined windows will be used in analysis.			
PROs	Baseline ^c	Day -7 to Day -1	≤ Day 5
	Week 4	Day 29	Days [6, 57]
	Week 12	Day 85	Days [58, 134]
	Week 26	Day 183	Days [135, 274]
	Week 52	Day 365	Days [275, 448]
	Week 76	Day 533	Days [449, 630]
	Week 104/EY	Day 730	Days [631, 812]
	Week 128	Day 897	Days [813, 994]
	Week 156/EY	Day 1096	Days [995, 1176]
	Week 180	Day 1261	Days [1177, 1358]
	Week 208/EY	Day 1461	Days [1359, 1540]
	Week 232	Day 1625	Days [1541, 1722]
Week 260/EY	Day 1826	Days [1723, 1840]	
PBMC (ELISpot)	Baseline ^c	Day -7 to Day -1	≤ Day 1
	Week 2	Day 15	Days [2, 22]
	Week 4	Day 29	Days [23, 36]
	Week 6	Day 43	Days [37, 40]
	Week 8	Day 57	Days [41, 64]
	Week 10	Day 71	Days [65, 78]
	Week 12	Day 85	Days [79, 92]
	Week 14	Day 99	Days [93, 106]
	Week 16	Day 113	Days [107, 120]
	Week 18	Day 127	Days [121, 134]
	Week 20	Day 141	Days [135, 148]
	Week 22	Day 155	Days [149, 162]
	Week 24	Day 169	Days [163, 176]
	Week 26	Day 183	Days [177, 190]
	Week 28	Day 197	Days [191, 204]
	Week 30	Day 211	Days [205, 218]
	Week 32	Day 225	Days [219, 232]
	Week 34	Day 239	Days [233, 246]
Week 36	Day 253	Days [247, 281]	
Week 44	Day 309	Days [282, 337]	
Week 52	Day 365	Days [338, 393]	

	Study 270-301 Statistical Analysis Plan
---	--

Assessment	Derived Visit	Scheduled Visit Day ^a	Window ^b
	Week 64	Day 449	Days [408, 491]
	Week 76	Day 533	Days [492, 575]
	Week 88	Day 617	Days [576, 659]
	Week 100	Day 701	Days [660, 715]
	Week 104/EY	Day 730	Days [716, 772]
	Week 116	Day 814	Days [773, 856]
	Week 128	Day 898	Days [857, 940]
	Week 140	Day 982	Days [941, 1024]
	Week 152	Day 1066	Days [1025, 1080]
	Week 156/EY	Day 1096	Days [1081, 1138]
	Week 168	Day 1180	Days [1139, 1222]
	Week 180	Day 1264	Days [1223, 1306]
	Week 192	Day 1348	Days [1307, 1390]
	Week 204	Day 1432	Days [1391, 1446]
	Week 208/EY	Day 1461	Days [1447, 1503]
	Week 220	Day 1545	Days [1504, 1587]
	Week 232	Day 1629	Days [1588, 1671]
	Week 244	Day 1713	Days [1672, 1755]
	Week 256	Day 1797	Days [1756, 1811]
	Week 260/EY	Day 1826	Days [1812, 1840]
Liver tests, Vital signs, and other central lab tests	Baseline ^c	Day -1	≤ Day 1
	Week 1	Day 8	Days [2, 11]
	Week 2	Day 15	Days [12, 18]
	Week 3	Day 22	Days [19, 25]
	Week 4	Day 29	Days [26, 32]
	Week 5	Day 36	Days [33, 39]
	Week 6	Day 43	Days [40, 46]
	Week 7	Day 50	Days [47, 53]
	Week 8	Day 57	Days [54, 60]
	Week 9	Day 64	Days [61, 67]
	Week 10	Day 71	Days [68, 74]
	Week 11	Day 78	Days [75, 81]
	Week 12	Day 85	Days [82, 88]
	Week 13	Day 92	Days [89, 95]
	Week 14	Day 99	Days [96, 102]
	Week 15	Day 106	Days [103, 109]
	Week 16	Day 113	Days [110, 116]

	Study 270-301 Statistical Analysis Plan
---	--

Assessment	Derived Visit	Scheduled Visit Day ^a	Window ^b
	Week 17	Day 120	Days [117, 123]
	Week 18	Day 127	Days [124, 130]
	Week 19	Day 134	Days [131, 137]
	Week 20	Day 141	Days [138, 144]
	Week 21	Day 148	Days [145, 151]
	Week 22	Day 155	Days [152, 158]
	Week 23	Day 162	Days [159, 165]
	Week 24	Day 169	Days [166, 172]
	Week 25	Day 176	Days [173, 179]
	Week 26	Day 183	Days [180, 186]
	Week 27	Day 190	Days [187, 193]
	Week 28	Day 197	Days [194, 200]
	Week 29	Day 204	Days [201, 207]
	Week 30	Day 211	Days [208, 214]
	Week 31	Day 218	Days [215, 221]
	Week 32	Day 225	Days [222, 228]
	Week 33	Day 232	Days [229, 235]
	Week 34	Day 239	Days [236, 242]
	Week 35	Day 246	Days [243, 249]
	Week 36	Day 253	Days [250, 259]
	Week 38	Day 267	Days [260, 273]
	Week 40	Day 281	Days [274, 287]
	Week 42	Day 295	Days [288, 301]
	Week 44	Day 309	Days [302, 315]
	Week 46	Day 323	Days [316, 329]
	Week 48	Day 337	Days [330, 343]
	Week 50	Day 351	Days [344, 357]
	Week 52	Day 365	Days [358, 371]
	Week 56	Day 393	Days [372, 406]
	Week 60	Day 421	Days [407, 434]
	Week 64	Day 449	Days [435, 462]
	Week 68	Day 477	Days [463, 490]
	Week 72	Day 505	Days [491, 518]
	Week 76	Day 533	Days [519, 546]
	Week 80	Day 561	Days [547, 574]
	Week 84	Day 589	Days [575, 602]
	Week 88	Day 617	Days [603, 630]
	Week 92	Day 645	Days [631, 658]

	Study 270-301 Statistical Analysis Plan
---	--

Assessment	Derived Visit	Scheduled Visit Day ^a	Window ^b
	Week 96	Day 673	Days [659, 686]
	Week 100	Day 701	Days [687, 714]
	Week 104/EY	Day 730	Days [715, 743]
	Week 110	Day 772	Days [744, 792]
	Week 116	Day 814	Days [793, 835]
	Week 122	Day 856	Days [836, 877]
	Week 128	Day 898	Days [878, 919]
	Week 134	Day 940	Days [920, 961]
	Week 140	Day 982	Days [962, 1003]
	Week 146	Day 1024	Days [1004, 1045]
	Week 152	Day 1066	Days [1046, 1079]
	Week 156/EY	Day 1096	Days [1080, 1117]
	Week 162	Day 1138	Days [1118, 1159]
	Week 168	Day 1180	Days [1160, 1201]
	Week 174	Day 1222	Days [1202, 1243]
	Week 180	Day 1264	Days [1244, 1285]
	Week 186	Day 1306	Days [1286, 1327]
	Week 192	Day 1348	Days [1328, 1369]
	Week 198	Day 1390	Days [1370, 1411]
	Week 204	Day 1432	Days [1412, 1446]
	Week 208/EY	Day 1461	Days [1447, 1482]
	Week 214	Day 1503	Days [1483, 1524]
	Week 220	Day 1545	Days [1525, 1566]
	Week 226	Day 1587	Days [1567, 1608]
	Week 232	Day 1629	Days [1609, 1650]
	Week 238	Day 1671	Days [1651, 1692]
	Week 244	Day 1713	Days [1693, 1734]
	Week 250	Day 1755	Days [1735, 1776]
	Week 256	Day 1797	Days [1777, 1811]
	Week 260/EY	Day 1826	Days [1812, 1840]

^a Relative to the BMN 270 infusion day (Day 1)

^b Visit day is calculated as (visit date – date of infusion date + 1) if post infusion and (visit date – date of infusion date) if before infusion

^c Baseline visit value of FVIII activity is defined as the last available measurement prior to BMN 270 dosing excluding those within 72 hours after a FVIII infusion. Baseline visit value of other assessments is defined as the last available measurement prior to BMN 270 dosing.

^d For subjects enrolled from Study 270-902, the baseline value is derived from the period between the 270-902 enrollment day and the BMN 270 infusion day. For subjects not entering from 270-902, the baseline value is derived from the period between 12 months prior to 270-301 screening and the BMN 270 infusion day.

EY: end of year visit.

	
Study 270-301 Statistical Analysis Plan

---	--

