5.4 Visit Windows for Analysis

All efficacy and safety data will be summarized by week or by a duration of multiple weeks based on windows defined on study days, wherever applicable. An assessment for a subject will be classified according to the study day of the assessment where it falls within a given window (see Appendix 20.1 Visit Windows).

For the primary, secondary, and other efficacy endpoints, windows of multiple weeks are defined based on ranges of study days. Median, mean assessments, or annualized values from these windows may be used in efficacy analyses as deemed appropriate (see Section 13).

For the tertiary efficacy endpoints and safety endpoints, such as liver function tests and vital signs, the windows are designated for each scheduled week of visit and centered on a target day; for example, the target day for a Week 4 visit is Study Day 29. If there are two or more assessments within a designated window, the assessment that is closest to the target day will be used for analyses. If the two closest assessments to the target day are equidistant from the target day, then the mean of the two assessments will be used for analyses unless otherwise specified.

Appendix 20.1 Visit Windows lists the weeks assigned for the analyses of the clinical endpoint assessments and the corresponding range of treatment days (window) during which a visit may have occurred by analysis parameter.

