Cellular immunity in the form of cytotoxic T lymphocytes (CTL) will be evaluated by Interferon-gamma (IFN- γ) ELISpot assay of peripheral blood mononuclear cells (PBMC). PBMC will be stimulated with overlapping peptide pools derived from the AAV5 capsid protein or human FVIII protein sequences to evaluate IFN- γ secretion by CTL targeting both the AAV5 capsid and the FVIII transgene product. Cellular immunity will be evaluated at baseline and at post-infusion visits according to the protocol's schedule of events and is reported positive or negative by peptide pool stimulation and as spot forming units (SFU) per 10^6 PBMC. Test results will be summarized and data listings will be generated reporting positive or negative and the number of SFU 10^6 PBMC for each peptide pool and control stimulation for each patient at each study visit tested. Positive and negative results with the number of SFU per 10^6 PBMC will be evaluated for correlations with FVIII activity measures, changes in clinical chemistry or adverse events as appropriate for the data collected.

Study 270-301 Statistical Analysis Plan

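### The ELISpot Week 6 window (Days 37 to 40) excludes its own target Day 43, so on-schedule Week 6 samples are classed as Week 8 in by-visit summaries

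*SAP*

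**What the plan says.** SAP Appendix 20.1 (Visit Windows) lists a target day and a window for each derived ELISpot visit. The row at issue reads "Week 6 Day 43 Days [37, 40". The visit that follows it takes up the days from there, with "Week 8 Day 57 Days [41, 64". For comparison, the visit before this pair has "Week 4 Day 29 Days [23, 36", and the visit after the pair has "Week 10 Day 71 Days [65, 78".

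Section 5.4 (Visit Windows for Analysis) says how the table is used. On assignment: "An assessment for a subject will be classified according to the study day of the assessment where it falls within a given window". On construction, for tertiary and safety endpoints: "the windows are designated for each scheduled week of visit and centered on a target day". When a window holds two or more assessments, "the assessment that is closest to the target day will be used for analyses".

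The SAP synopsis lists immune response to the transgene product and the capsid among the safety endpoints, and Section 14 counts immunogenicity among the safety assessments. The Section 5.4 rules for safety endpoints therefore reach ELISpot. Section 15 (Immunogenicity Assessment) says the ELISpot results will be summarized. It also provides for listings of positive or negative status and "the number of SFU 10^6 PBMC for each peptide pool and control stimulation for each patient at each study visit tested".

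**The concern.** A visit window should contain the day on which the visit is scheduled. The Week 6 ELISpot window does not: it covers only days that are three to six days early, and the scheduled day belongs to the next visit. A programmer who follows the table literally would move on-schedule Week 6 samples to Week 8, where they compete with the real Week 8 sample and normally lose.

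What is at stake is the by-visit description of T-cell responses to capsid and FVIII at one early time point. A reader of the summary could take a thin Week 6 row to mean that few samples were collected, when they had been collected and assigned elsewhere. For a subject without a Week 8 sample, the value shown at Week 8 could be a Week 6 value.

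**Working it through.** **Inputs.** Target days and windows for the 40 post-baseline ELISpot rows (Appendix 20.1); the classification and closest-to-target rules (Section 5.4).

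**1. Does each window contain its target?** In 39 of the 40 rows it does. Week 6 is the exception: the target is Day 43 and the window is Days 37 to 40. Day 43 lies only in the Week 8 window, Days 41 to 64.

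**2. Window lengths.** Length = last day − first day + 1.

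| Visit | Target | Printed window | Length in days |
|---|---|---|---|
| Week 4 | 29 | 23 to 36 | 14 |
| Week 6 | 43 | 37 to 40 | 4 |
| Week 8 | 57 | 41 to 64 | 24 |
| Week 10 | 71 | 65 to 78 | 14 |

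**3. Which boundary does the table imply?** Compare each upper bound with the midpoint between its own target and the next target. From Week 2 to Week 36 there are 17 boundaries between visits two weeks apart, and 16 equal the midpoint exactly. For example, Week 4 to 6 is (29 + 43)/2 = 36, and Week 8 to 10 is (57 + 71)/2 = 64. The exception is Week 6 to 8: (43 + 57)/2 = 50, against a printed 40, a difference of 10 days. With the boundary at Day 50, Week 6 is Days 37 to 50 and Week 8 is Days 51 to 64, each 14 days long.

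The liver-test and laboratory rows of the same appendix also have a Week 6 target of Day 43. Their window, Days 40 to 46, contains it.

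**4. What happens to a Week 6 sample under Section 5.4?**

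- A sample on Day 43 is classed as Week 8 and lies 57 − 43 = 14 days from that target.
- Any other sample on Days 44 to 64 is at most 13 days from Day 57, so it is the one used in the windowed analysis.
- If the subject has no other sample in the window, the Day 43 result is reported as Week 8.
- Days 41 to 49 are all nearer to Day 43 than to Day 57, yet all are assigned to Week 8. Day 50 is equidistant.

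**5. How many samples reach Week 6?** None drawn within two days of target (Days 41 to 45). Beyond that, an assumption about visit timing is needed. If visit days were spread evenly over:

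- ±3 days (Days 40 to 46): only Day 40 qualifies, 1/7 = 14%.
- ±5 days (Days 38 to 48): Days 38 to 40 qualify, 3/11 = 27%.
- ±7 days (Days 36 to 50): Days 37 to 40 qualify, 4/15 = 27%.

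These shares are illustrative. The SAP gives neither a tolerance nor a distribution for ELISpot visit days.

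**6. The other break in the table.** Week 52 ends on Day 393 and Week 64 starts on Day 408, which leaves 408 − 393 − 1 = 14 days (394 to 407) unassigned. The midpoint is (365 + 449)/2 = 407. Day 394 is 29 days after the Week 52 target and Day 407 is 42 days before the Week 64 target, and no ELISpot visit is scheduled between the two. Apart from Weeks 6 and 52, every upper bound with a following visit is within one day of the midpoint.

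**The case against.** **Possible misprint in the text.** The tables were read from PDF, so a misread digit is conceivable. But two separate cells agree: Week 6 ends at 40 and Week 8 starts at 41. One misread digit would have left a gap or an overlap. This objection does not stand.

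**Windows are not literally centred.** This is true. Week 2 (Days 2 to 22 around Day 15) and Week 36 (Days 247 to 281 around Day 253) are off-centre because visit spacing changes there. Lack of centring is therefore not the error. The error is that the target lies outside its window and the boundary breaks the midpoint pattern that every other two-weekly boundary follows.

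**Stronger readings that the SAP does not support.**

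- A reader might infer that Week 6 results are lost. The closest-to-target rule selects values for analyses and is not stated to remove results from listings. Section 15 provides listings of every visit tested. Exclusion is confined to windowed summaries, and needs a second sample closer to Day 57 in the Week 8 window.
- A reader might infer a hole in immune monitoring around Week 6. The windows run without a break from Day 2 to Day 393, so every sample on Days 37 to 64 is assigned. The fault is a wrong label and a thin row.
- A reader might infer distorted correlations with FVIII activity, chemistry or adverse events. Section 15 plans such correlations as appropriate for the data collected and does not say that they use windowed visit values.
- A reader might infer that tables already produced are wrong. The SAP does not show which windows the programs used.

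**Weight.** Section 15 calls the immunological analysis primarily descriptive, and Section 14 says no formal safety testing is done. This stands, and it keeps the point minor.

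**Conclusion.** The table is wrong as written. If it is followed, ELISpot samples from Days 41 to 45 are classed as Week 8, and only samples taken three to six days early fill the Week 6 row. That conclusion needs only the printed rows and Section 5.4. Whether a given sample then drops out of the summary depends on the subject also having a sample closer to Day 57, which is the expected case when both visits are kept. The share of samples captured by the printed window cannot be fixed from the SAP.

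The effect is limited to one time point of a descriptive assay. No hypothesis test, alpha allocation, or primary or secondary endpoint depends on it. The Day 394 to 407 gap is real but marginal, since it affects only samples far from any scheduled ELISpot visit. Severity is minor.

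**What to change.** In the PBMC (ELISpot) rows of Appendix 20.1, following the table's own midpoint pattern:

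- set Week 6 to Days 37 to 50;
- set Week 8 to Days 51 to 64;
- end Week 52 on Day 407, so that it meets the Week 64 window starting on Day 408.

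Confirm which windows the analysis programs used. If they applied the printed ones, re-run the descriptive ELISpot by-visit tables. If they already used Day 50, record that, so that the written specification and the output agree.

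The cost is three edited rows, one check of the programs and, at most, a re-run of descriptive tables. No new data are needed. Because the windows run to Week 260 and follow-up continues for about 5 years, the correction also serves any later use of the table.

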20.2 Preferred Terms Suggestive of Thromboembolic Events

confusional state (10010305)
muscular weakness (10028372)
swelling (10042674)
peripheral swelling(10048959)
odema Peripheral (10030124)
jaundice (10023126)
urine output decreased (10059895)
pain in extremity (10033425)
erythema (10015150)
dyspnea (10013968)
chest pain (10008479)
chest discomfort (10008469)
tachycardia (10043071)
haemoptysis (10018964)
presyncope (10036653)
headache (10019211)
hypoesthesia (10020937)
eye pain (10015958)
eye swelling (10015967)
visual impairment (10047571)
visual acuity reduced (10047531)

Signature Page for VV-CLIN-002753 v2.0

Approval	PI [redacted] PI [redacted], BioStatistics 10-Dec-2021 19:31:04 GMT+0000
----------	--

Approval	PI [redacted] PI [redacted], Clinical Science 10-Dec-2021 19:36:33 GMT+0000
----------	---

Approval	PI [redacted] PI [redacted], Biostatistics 10-Dec-2021 20:27:37 GMT+0000
----------	--

Approval	PI [redacted] Principal Statistical Programmer 2 10-Dec-2021 22:11:54 GMT+0000
----------	--

Approval	PI [redacted] PI [redacted], Clinical Science 13-Dec-2021 07:30:39 GMT+0000
----------	---

Approval	PI [redacted] PI [redacted] 13-Dec-2021 19:47:28 GMT+0000
----------	---

Signature Page for VV-CLIN-002753 v2.0
